8 COMPLETION, WITHDRAWAL AND TERMINATION CRITERIA

8.1 Completion

8.1.1 Definition of completed subject

A completed subject is one who has completed all imaging sequences of the combined [18F]FPIA PET/MRI protocol.

8.1.2 Definition of an evaluable subject

An evaluable subject is one who has completed study and where the images from the [18F]FPIA PET/MRI are of sufficient quality for analysis.

In the case of subject withdrawal or non-evaluable subjects before or after dosing, additional subjects will be enrolled to reach 24 evaluable subjects.

8.1.3 Time on study

The last study related visit for a subject would be the PET/MRI scan. There are no follow up patient visits unless follow up for resolution of Adverse Events is required.

Depending on the screening period taken in relation to the scan day, a subject can be on study between 2 and 23 days including a 24 hour post scan reportable Adverse event period.

8.2 Rules for subject withdrawal

There are no formal withdrawal criteria for this study. During the conduct of the study, the study team will review the safety data for trends and signals that would indicate the need for withdrawal of a subject.

In accordance with the Declaration of Helsinki, each subject is free to withdraw from the study at any time. Investigator(s) also have the right to withdraw subjects from the study in the event of illness, AEs, or other reasons concerning the health or well-being of the subject, or in the case of lack of co-operation. Should a subject decide to withdraw after administration of the tracer, or should the investigator decide to withdraw the subject, all efforts will be made to complete and report the observations up to the time of withdrawal as thoroughly as possible. A complete final evaluation at the time of the subject's withdrawal will be made and an explanation given of why the subject is withdrawing or being withdrawn from the study.

The reason for non-completion and the date and time of the last contact with the subject must be noted in the research documentation. If the reason for withdrawal is a clinical AE or an abnormal laboratory result, monitoring will continue until the outcome is evident. The specific event or test result(s) must be recorded in the research documentation. In the case of subject withdrawal before or after dosing (i.e., non-evaluable subjects) additional subjects may be enrolled to reach a total of 24 evaluable subjects.

8.3 Rules for terminating study

The sponsor reserves the right to terminate the study at any time. Prior to dosing of the first subject, the study may be terminated by the sponsor and the investigator

FPIA METS_PROTOCOL_V2.0_08APR2022

without consultation with the Administration of Radioactive Substances Advisory Committee (ARSAC) holder and Ethics Committee. The ARSAC holder, Ethics Committee and Health Research Authority (HRA), must be promptly notified that the study will no longer be taking place and provided with a detailed written explanation. Once dosing with radiopharmaceutical has begun, the study may only be terminated if a careful review of the overall risk benefit analysis demonstrates that the assumptions have changed and that the overall balance is no longer acceptable. The investigators will temporarily halt the study if there has been a SAE which has been judged to be related to the study dosing. In these circumstances' termination can only take place with the agreement of the Sponsor, ARSAC holder and the Ethics Committee.

If it becomes necessary to consider termination of the study after dosing has begun, dosing may be suspended pending discussion between the sponsor, the investigator, the ARSAC holder and the Ethics Committee. Dosing may always be immediately suspended for safety reasons.

8.4 End of Study

The end of the study is defined as the last visit of the last patient undergoing the study.

9 RADIOTRACER AND IMAGING

9.1 Radiopharmaceutical

The [18F]FPIA radiotracer will be made to GMP standards at the Good Manufacturing Practice (GMP) Facility, University College London.

Due to the short half-life of [18F]FPIA, the supply will be provided on a per-patient basis.

[¹⁸F]FPIA will be packaged labelled and distributed by an appropriate courier to Invicro by the GMP Facility, University College London. Labels will be prepared in accordance with Good Manufacturing Practice Annex 13 requirements and local regulatory guidelines.

The investigators are responsible for ensuring that deliveries of the tracer and study material are correctly received, recorded, handled and stored safely and

properly, in accordance with regulatory guidelines (ICH-GCP and Good Manufacturing Practice (GMP) and used in accordance with this protocol.

9.2 Imaging Protocol

- Patients taking part in this study will have either one or two [18F]FPIA PET/MRI scans
- ¹⁸F-FPIA PET/MRI imaging will be carried out at the Hammersmith Hospital site, within Invicro.
- Pre-scan assessments will be carried out as per Table 1.
- A peripheral venous cannula will be inserted within the arm for radiotracer and MRI contrast injections.
- Simultaneous [¹⁸F]FPIA PET and MRI whole brain imaging (single bed position over the whole brain from vertex).
- Following completion of imaging, the venous cannula will be removed at the end of the scan and patient will be discharged.
- AEs will be reportable for up to 24 hours after the scan.

9.3 PET Protocol

- For the PET scan, a maximum of 370 MBq [¹⁸F]FPIA will be injected followed by a saline flush per scan.
- PET data will be acquired immediately after tracer injection as a single-bed position (single bed position over the whole brain from vertex) with a dynamic imaging scan duration of 66 minutes.

9.4 MRI Protocol

The MRI protocol will include the following sequences:

- Sequences for attenuation correction of PET data (DIXON, zero-TE)
- Volumetric T1-weighted images, pre- and post-contrast administration
- Volumetric T2
- Dynamic susceptibility contrast perfusion (DSC)
- Dynamic contrast enhanced perfusion (DCE)

The exact image acquisition parameters for sequences (e.g. TE, TR, flip angle) are hardware dependent and vary between scanner manufacturers and models, and are therefore not specified here. DWI sequences will be acquired prior to contrast agent administration.

9.6 Radiation dose

Each patient that participates in this study will have up to two additional PET/MRI scan in addition to their standard of care. If the patient is having radiotherapy (SRS) as part of their standard of care, the radiation dose estimated is 12-35Gy in 1-5 fractions.

For each PET MRI, simultaneous ¹⁸F-FPIA PET and MRI whole brain imaging (vertex to C1 vertebral body) will be performed.

There is no ionizing radiation from the MR component of the study only from the one PET scan.

The maximum additional radiation dose associated with having 1 [18F]FPIA PET scan and is estimated to be 5.7mSv (from an administered activity of 370MBq of [18F]FPIA -which is similar to other common 18F PET imaging tracers).

The radiation dose required by the study is additional to routine clinical care. The total protocol dose is 5.7mSv per scan. This is equivalent to 2 years and 6 months of average natural background radiation in the UK. If you have 2 scans as part of this study, the total dose you will receive is 11.4 mSv, which is equivalent to 5 years of the average natural background radiation in the UK. Ionising radiation can cause cancer which manifests itself after many years or decades. The risk of developing cancer as a consequence of taking part in this study is estimated as 0.03% (1 in 3,510) for one scan, and 0.06% (1 in 1,755) for 2 scans.

For comparison, the natural lifetime cancer incidence in the general population is about 50% (1 in 2).

For the patients having radiotherapy, the radiation dose from the [18F]FPIA PET/MRI scan will be very small compared to radiotherapy.

9.7 Imaging Complications

There are no immediate complications anticipated of the PET/MRI scan except for a potential mild bruising at the site of insertion of the peripheral cannula which should resolve within a few days. Rarely, the participant feel may dizzy after the scan due to lying flat but this is normally short lived.

MRI scanners use strong magnets, and therefore the subject will be given a safety questionnaire to complete and the study personnel will ask questions to make sure that you can safely have an MRI scan. As the MRI is noisy the subject will be given ear protection to wear. There is a risk of claustrophobia (fear of being in small places) associated with the scanner.

A contrast agent (Gadolinium) will be used for the MRI scans which is injected intravenously. Some studies have shown gadolinium deposits in the brain and other tissues when using gadolinium contrast agents. There is no evidence that FPIA METS_PROTOCOL_V2.0_08APR2022 CONFIDENTIAL

this has caused any harm to patients and recommendations by the European Medicines Agency to use contrast agents with a lower risk of gadolinium deposition will be followed.

Scans will be stopped at any time during the procedure if the subject is unable to tolerate it.

10 ADVERSE EVENTS

10.1 Definitions

Adverse Event (AE): any untoward medical occurrence in a patient or clinical study subject.

Serious Adverse Event (SAE): any untoward and unexpected medical occurrence or effect that:

- Results in death;
- Is life-threatening*;
- Requires hospitalisation or prolongation of existing inpatient's hospitalisation**;
- Results in persistent or significant disability or incapacity;
- Is a congenital abnormality or birth defect;
- * "Life-threatening" in the definition of "serious" refers to an event in which the patient was at risk of death at the time of the event; it does not refer to an event which hypothetically might have caused death if it were more severe.
- ** "Hospitalisation" means any unexpected admission to a hospital department. It does not usually apply to scheduled admissions that were planned before study inclusion or visits to casualty (without admission).

Medical judgement should be exercised in deciding whether an adverse event/reaction is serious in other situations. Important adverse events/reactions that are not immediately life-threatening, or do not result in death or hospitalisation but may jeopardise a patient or may require intervention to prevent one of the other outcomes listed in the definition above should also be considered serious.

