10.2.2 Serious AEs

An SAE form should be sent to the Chief Investigator with 24 hours. However, relapse, death and/or hospitalisations for elective treatment of a pre-existing condition do not need reporting as SAEs.

All SAEs will be reviewed by the Chief Investigator or a designated medically qualified representative to confirm expectedness and causality.

All SAEs should be reported to the relevant REC where in the opinion of the Chief Investigator, the event was:

- 'Related', i.e. resulted from the administration of any of the research procedures; and
- 'Unexpected', i.e. an event that is not listed in the protocol as an expected occurrence

Reports of related and unexpected SAEs should be submitted within 15 days of the Chief Investigator becoming aware of the event, using the NRES SAE form for non-IMP studies. The Chief Investigator must also notify the Sponsor of all SAEs.

Local investigators should report any SAEs as required by their Local Research Ethics Committee, Sponsor and/or Research & Development Office.

Please send SAE forms to the Sponsor and CI to the below email addresses:

Contact details for reporting SAEs are as follows:

[contact] (Sponsor E-mail)
[contact](CI E-mail)
[contact]

Please send SAE forms to the Sponsor and CI on the above email addresses:

(Mon to Fri 09.00 -17.00)

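### Section 10.1 makes 'unexpected' part of the SAE definition, contradicting 10.2.2, so a listed event that turns serious need not be handled as an SAE

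*Combined protocol and SAP*

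**What the plan says.** Section 10.1 defines an AE as "any untoward medical occurrence in a patient or clinical study subject", with no condition on expectedness. It defines an SAE more narrowly, as "any untoward and unexpected medical occurrence or effect that" meets one of the listed criteria: death, threat to life, hospitalisation, lasting disability or a birth defect.

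Section 10.2.2 sets out what follows from an SAE:

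- "An SAE form should be sent to the Chief Investigator with 24 hours".
- "All SAEs will be reviewed by the Chief Investigator or a designated medically qualified representative to confirm expectedness and causality".
- "The Chief Investigator must also notify the Sponsor of all SAEs".
- A report goes to the REC only if the event is both related and unexpected. Unexpected is explained there as "an event that is not listed in the protocol as an expected occurrence".

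Section 8.3 adds one more consequence: "The investigators will temporarily halt the study if there has been a SAE which has been judged to be related to the study dosing".

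Section 9.7 lists the foreseeable imaging complications: mild bruising at the cannula site, rare dizziness "due to lying flat but this is normally short lived", claustrophobia in the scanner, and gadolinium deposition without evidence of harm.

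**The concern.** Seriousness and expectedness are separate judgements. Section 10.2.2 keeps them apart: an event becomes an SAE, a medically qualified person then decides whether it was expected, and that decision affects only onward reporting to the REC. Section 10.1 merges them by making unexpectedness a condition of entry.

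The escalation steps are all keyed to the term SAE. If a serious event of a listed type never receives that label, the steps are not required for it. The expectedness decision also moves from the Chief Investigator or medical delegate to whoever at the site decides whether to complete a form. Prompt escalation carries weight in this study because the protocol describes it as the first use of the tracer in patients with cerebral metastases, there are no routine follow-up visits, and AEs are reportable for only 24 hours after a scan.

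**Working it through.** No sample size, error rate or event count enters this point, and the plan gives no figure to reproduce. The check is to follow the definition through every rule that uses the term SAE.

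**Step 1: consistency.** Suppose every SAE is unexpected, as 10.1 requires. The review of expectedness in 10.2.2 then has only one possible answer, and the REC condition of related and unexpected reduces to related. Both provisions make sense only if some SAEs are expected, which 10.1 rules out.

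**Step 2: meaning of the word.** The only explanation of an unexpected event is the one in 10.2.2, an event not listed in the protocol. The hospitalisation footnote in 10.1 also uses the word, but there it describes the admission, not the type of event.

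**Step 3: cases.**

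| Event | Listed as expected? | SAE under literal 10.1? | SAE under the 10.2.2 process? |
|---|---|---|---|
| Post-scan dizziness that itself leads to an unplanned admission | Yes (9.7) | No | Yes |
| Injury from a fall, with admission | No | Yes | Yes |
| Acute serious reaction to the tracer | No | Yes | Yes |

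Only the first row differs. Under 10.2.2 that event would go on a form to the Chief Investigator, be judged expected, go to the Sponsor and stop short of the REC. Under 10.1 it is an AE only.

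Radiation-induced cancer, named in 9.6, is left out of the table because it would appear years later, far outside the AE window.

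**Step 4: does any clause bring the first row back?**

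- The medical-judgement paragraph in 10.1 widens what counts as serious in situations the list does not cover. It does not lift the expectedness condition from an event that already meets a listed criterion.
- The reporting exemptions in 10.2.2 (relapse, death, elective hospitalisation) take events out and restore none. They are a separate matter, and this point does not rely on them.

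**Step 5: what is lost for the first row.** Three mandatory steps are lost: the 24-hour form, the expectedness and causality review, and Sponsor notification. The halt in 8.3 is a fourth rule keyed to the term SAE, but it also requires a relation to dosing. Section 9.7 attributes the dizziness to posture, and no acute reaction to the tracer is listed anywhere. The documents therefore supply no listed acute event that would escape the halt.

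**The case against.** The strongest reply is that this is a drafting slip with little practical effect. Section 10.2.2 shows the intended route plainly, and a sensible site would follow it. The listed acute complications are mild, short-lived or not described as serious. Nothing disappears from view: all AEs are collected up to 24 hours after each scan and unresolved ones are followed up (10.2.1), the team's review of safety data in 8.2 is not confined to SAEs, and 8.3 lets dosing be suspended at once on safety grounds without reference to SAE status.

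Most of this stands, and it limits the point. It does not remove the contradiction, because a site that applies the definition as written and a site that follows the process as written would report the same event differently.

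A reader might infer more than the documents support:

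- **That the halt in 8.3 is disabled for tracer reactions.** It is not. An acute serious tracer reaction is unlisted, so it is unexpected and counts as an SAE under either section.
- **That a dizzy patient who falls and is admitted drops out of SAE reporting.** The injury is not a listed occurrence, so it qualifies as an SAE. The case that fails is admission for the dizziness itself.
- **That a run of such events could not reach anyone able to stop dosing.** A compulsory trigger is lost. Visibility and the power to suspend are not.
- **That the gap can be expressed as a rate.** Saying that none of the affected events enter the SAE route merely restates the definition.

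**Conclusion.** The contradiction between 10.1 and 10.2.2 is real, and no other clause resolves it. Taken literally, 10.1 removes a listed event that becomes serious from three compulsory steps and leaves the site to judge expectedness before any form exists. The effect on the 8.3 halt is small or nil.

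The number of events affected cannot be estimated, because the documents give no rates for the listed complications and describe none of the acute ones as serious. The conclusion assumes that 'unexpected' in 10.1 carries the meaning given in 10.2.2. If staff read it in the ordinary clinical sense, as anything foreseeable in patients with brain metastases, the exclusion would be wider. The documents neither state nor rule out that reading, so no weight is placed on it here.

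Severity: should be fixed. The documents do not support a higher grade.

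**What to change.** In the SAE definition in 10.1, delete the words 'and unexpected', so that meeting a seriousness criterion is what makes an untoward occurrence an SAE. Leave expectedness where 10.2.2 puts it: judged by the Chief Investigator or medical delegate after receipt, and used to select events for the REC. Then read 10.1, 10.2.2 and 8.3 together and have the sponsor confirm that the term SAE means the same in all three, including in the halt rule. This review does not propose what the halt rule should be.

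The cost is a two-word change in an amendment and a few more forms to the Chief Investigator and Sponsor. The REC criteria stay the same, but REC volume could rise slightly: some events a site would have screened out as expected will now reach the Chief Investigator, who may judge an occasional one related and unexpected.

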10.2 Reporting of Adverse Events

10.2.1 Non serious AEs

AEs will be collected from the start of each scan visit to up to 24 hours after each PET/CT scan.

Any AEs which remain unresolved at the patient's last visit in the study should be followed up by the Investigator for as long as medically indicated.

Depending on the nature of the event the reporting procedures below should be followed. Any questions concerning adverse event reporting should be directed to the Chief Investigator in the first instance

10.2.2 Serious AEs

An SAE form should be sent to the Chief Investigator with 24 hours. However, relapse, death and/or hospitalisations for elective treatment of a pre-existing condition do not need reporting as SAEs.

All SAEs will be reviewed by the Chief Investigator or a designated medically qualified representative to confirm expectedness and causality.

All SAEs should be reported to the relevant REC where in the opinion of the Chief Investigator, the event was:

- 'Related', i.e. resulted from the administration of any of the research procedures; and
- 'Unexpected', i.e. an event that is not listed in the protocol as an expected occurrence

Reports of related and unexpected SAEs should be submitted within 15 days of the Chief Investigator becoming aware of the event, using the NRES SAE form for non-IMP studies. The Chief Investigator must also notify the Sponsor of all SAEs.

Local investigators should report any SAEs as required by their Local Research Ethics Committee, Sponsor and/or Research & Development Office.

Please send SAE forms to the Sponsor and CI to the below email addresses:

Contact details for reporting SAEs are as follows:

[contact] (Sponsor E-mail)
[contact](CI E-mail)
[contact]

Please send SAE forms to the Sponsor and CI on the above email addresses:

(Mon to Fri 09.00 -17.00)

11 STATISTICS AND DATA ANALYSES

11.1 Statistical Design

The study is an Observational Non-randomised Phase 2 study to determine the magnitude of the early steps of fatty acid oxidation in cerebral metastases using [18 F]FPIA PET/MRI. This is the first time we are using FPIA in patients (with cerebral metastases), thus we do not know *a priori* the magnitude of uptake. Statistical tests will use a 0.05 significance level and will be 2-sided unless otherwise noted. 24 evaluable patients will be recruited for the study with the Upper Confidence Interval of sensitivity to detect fatty acid metabolism set to \geq 90%.

11.2 PET Analysis

Dynamic PET attenuation corrected images will be reconstructed. Regions of interest (ROIs) corresponding to tumour and normal brain tissue will be drawn on summed images (e.g. 15-65 min), and used to generate. The ROIs will be used to derive semi-quantitative uptake parameters. These may include SUV_{mean} (mean of standardized uptake values (SUV) within an ROI) normalised to body weight (bw), SUV_{max} and SUV_{peak}.

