3.2.2 Hypothesis

We hypothesise that FPIA uptake will be higher in metastases that are treatment naïve compared to those that have undergone treatment, in keeping with viable tumour cells having a high propensity to generate ATP and NADPH via fatty acid oxidation under bioenergetic stress.

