5 STUDY OUTLINE

5.1 Study Overview

24 evaluable patients with radiological evidence of cerebral metastases on MRI will be enrolled into the study (12 who are treatment naïve + 12 who have completed SRS+/- combination therapy). The patients invited to participate in the study will provide written informed consent, but will only undergo [¹8F]FPIA PET/MRI imaging once they have satisfied the inclusion and exclusion criteria.. Once these have been satisfied, eligible patients will proceed to [¹8F]FPIA PET/MRI. The same treatment naiive patients, who have had one [¹8F]FPIA PET/MRI scan and completed SRS+/- combination therapy, may be invited to take part in a second [¹8F]FPIA PET/MRI scan, as long as they satisfy the inclusion and exlusion criteria.

On the day of imaging the patients will undergo a blood test to measure plasma concentrations of carnitine (approximately 6mls). During the scan, a single dose of [18F]FPIA (maximum, 370 MBq) IV will be administered to the participant followed by a whole brain dynamic PET/MRI scan over 66 minutes. During the MRI sequences, the patient will receive a 2 stage IV bolus of Gadolinium contrast medium administered through a peripheral venous cannula.

FPIA METS_PROTOCOL_V2.0_08APR2022

CONFIDENTIAL

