12.9 Subject Confidentiality

Imperial College London and Imperial College NHS Trust data protection policies will be followed. Subjects personal data will be available only to clinical and research members directly involved in the study conduct. The Chief Investigator will preserve the confidentiality of participants taking part in the study and is registered under the Data Protection Act.

Participants will be allocated a unique study identifier code which will be known to the study research team and staff. The study identifier code will be used to pseudonymise samples, results, datasets and scans which would be held electronically on Imperial College London computers.

Subjects' identification data will be required for the recruitment, screening and registration processes. On study documents submitted to the Sponsor, patients will be identified by a trial ID number only. Documents that are not submitted to the FPIA METS_PROTOCOL_V2.0_08APR2022 CONFIDENTIAL

Sponsor (e.g. signed informed consent form) will be kept in a strictly confidential file by the investigator.

The Chief Investigator shall permit direct access to patients' records and source document for the purposes of monitoring, auditing, or inspection by the Sponsor, authorised representatives of the Sponsor, Regulatory Authorities and REC.

Invicro. staff will have access to limited participants' personal data for registration, IRMER, safety and governance purposes but may need to view the participant's medical records in the event of any study adverse events or emergencies on the scan day. This would be for the period of an event only and under the jurisdiction of the study investigator.

The subject's GP will be informed of their participation in the study.

The taxi company will be given the name address & contact number of the subject by email or telephone.

12.10 Material Storage and Analysis.

Blood samples for renal function will be analysed by Imperial College Healthcare NHS Pathology department and identifiable results reported on a secure webbased results reporting system under the Imperial NHS Trust data protection policy, only accessible by NHS contracted staff.

Carnitine plasma samples will be pseudonymised & stored frozen at Imperial College London. They will be sent to an external hospital laboratory for analysis and will not be identifiable to laboratory personnel.

Urine samples for pregnancy testing will be pseudonymised and tested immediately by research staff.

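### Neither the drawing of tumour ROIs nor the decision that a scan is evaluable is masked to treatment group, which could bias the secondary naïve-versus-treated comparison in either direction

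*Combined protocol and SAP*

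**What the plan says.** Section 11.2 (PET Analysis): "Regions of interest (ROIs) corresponding to tumour and normal brain tissue will be drawn on summed images". The semi-quantitative uptake measures come from these ROIs. SUVmean, SUVmax and SUVpeak are listed as possibilities, and none is chosen. No reader, number of readers, boundary rule or masking is given.

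Section 8.1.2: a subject is evaluable if the study was completed and the images "are of sufficient quality for analysis". No criteria or assessor are named. Sections 6, 8.1.2 and 8.2 provide for replacement until 24 evaluable subjects are reached.

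Section 3.2.2: "We hypothesise that FPIA uptake will be higher in metastases that are treatment naïve compared to those that have undergone treatment". This contrast is the secondary endpoint (section 4.2.2), studied in non-randomised groups: "12 who are treatment naïve + 12 who have completed SRS+/- combination therapy" (section 5.1). Some naïve patients may return for a second scan after SRS.

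Two other provisions bear on the point. Section 12.9: "The study identifier code will be used to pseudonymise samples, results, datasets and scans". Section 11.4 plans semi-automated segmentation of tumour volumes on structural MRI.

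**The concern.** Two human decisions sit between the scan and the secondary result: where the tumour boundary is drawn, and whether the scan counts. A reader who knows the arm, or the same patient's earlier scan, and who shares the protocol's stated expectation may make either decision differently in the two groups. A generous outline on a treated lesion would lower its SUVmean. A treated scan with little uptake might be judged unusable and replaced, which would push the other way. With 12 patients per group and no randomisation, a small systematic difference in reading could create or erase a difference between groups.

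**Working it through.** **The plan's own figure.** The plan gives no figure for reader effect, uptake SD or expected difference. Its one numerical justification is in section 11.1: "24 evaluable patients will be recruited for the study with the Upper Confidence Interval of sensitivity to detect fatty acid metabolism set to" at least 90%. That basis concerns a sensitivity and not the group comparison, so it neither supports nor limits what follows.

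**Step 1: is masking provided anywhere?** Set side by side:
- Section 11.2 fixes how ROIs arise (drawn) but not by whom or with what knowledge.
- Section 8.1.2 fixes that quality decides inclusion but not who decides or by what criteria.
- Sections 12.9 and 13.1 pseudonymise scans. This removes identity; nothing says that it hides arm. Section 6.5 numbers subjects in order of inclusion, so the code does not itself reveal arm either.
- Section 11.4 applies semi-automated segmentation to MRI volumes and does not link those volumes to the PET ROIs.

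No provision masks either decision to treatment group.

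**Step 2: how far can the boundary move SUVmean?** Assumptions: uniform sphere of 10, 15 or 20 mm (section 6.3 admits targets from 1 cm), 0.75 mm voxels, Gaussian blur of 4-6 mm FWHM, and background as a fraction of lesion uptake. None of the imaging inputs is in the documents.

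Change = (mean within radius R + k) / (mean within radius R) − 1, for k = 1 or 2 mm.

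| Background / lesion | ROI 1 mm wider | ROI 2 mm wider |
|---|---|---|
| 20-40% | −7.0% to −16.5% | −13.7% to −32.0% |
| 60-80% | −1.9% to −6.7% | −3.7% to −13.0% |

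The change in SUVmax is 0% in every case, because the maximum lies inside both outlines. SUVpeak and the kinetic measures of section 11.3 were not modelled. The lower row is the relevant one for a low-uptake treated lesion, where contrast is poor.

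**Step 3: what would a differential shift do to the test?** Inputs: 12 per group (section 5.1) and α = 0.05, two-sided (section 11.1). No test is named, so a two-sample t-test on independent groups with equal SD is assumed.

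- Degrees of freedom: 12 + 12 − 2 = 22; critical t = 2.074.
- Smallest significant observed difference: 2.074 × √(1/12 + 1/12) = 0.85 SD.
- Rejection probability for a net difference δ in SD units: P(|T| > 2.074), where T is noncentral t with 22 df and noncentrality δ × √(12/2) = 2.449 δ.

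| True difference | Reader shift | Net δ | P(significant) |
|---|---|---|---|
| 0 | 0 | 0 | 0.050 |
| 0 | 0.10 towards hypothesis | 0.10 | 0.056 |
| 0 | 0.25 towards | 0.25 | 0.090 |
| 0 | 0.50 towards | 0.50 | 0.216 |
| 1.20 | 0 | 1.20 | 0.80 |
| 1.20 | 0.25 against | 0.95 | 0.60 |
| 1.20 | 0.50 against | 0.70 | 0.37 |

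**Step 4: evaluability alone.** In 100,000 simulated trials with no true difference, the single lowest naïve and single highest treated scan were rejected and replaced by fresh draws. Type I error was 0.128 (mean bias 0.27 SD). With two and two it was 0.263 (0.46 SD). Opposite rejection with a true 1.2 SD difference cut power from 0.80 to 0.67 (one and one) or 0.52 (two and two). These are worst cases, since they remove exactly the most extreme scans.

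**The case against.** The strongest reply is that silence is not open reading. The documents do not say that the reader will know the arm, and a reader might infer from this point that they do; that is not supported. What stands is that sections 11.2 and 8.1.2 are where masking would be committed to, and neither does so.

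A second reply is that SUVmax is insensitive to the outline, which the model confirms. But section 11.2 does not commit to SUVmax, and rejecting a scan can affect every measure.

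A third is that intensity-based MRI segmentation would narrow the discretion. It would if it set the PET ROIs, but section 11.4 does not say so, and the method remains only semi-automated.

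A fourth is that the study is exploratory and section 11.1 says that "Statistical tests will use a 0.05 significance level and will be 2-sided unless otherwise noted". So it would be wrong to infer a one-sided test from the directional hypothesis. Two-sided testing does not, however, correct a biased measurement.

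Two stronger readings fail. One is that such bias could never be detected later: section 13.1 keeps data for ten years, so a masked re-read of stored scans could look for it. No section says that ROI files are kept, however, and section 8.2's requirement to record reasons for non-completion does not clearly cover a completed scan rejected for quality. The other is that a 1-2 mm drawing habit equals a treatment effect of some recognised size. Without an SD for uptake, a percentage change in SUVmean cannot be turned into an effect size.

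**Conclusion.** The point holds for the secondary comparison: neither ROI drawing nor the evaluability decision is masked to treatment group, and the protocol states the direction that it expects. Bias is possible in either direction; it is not shown to occur. Knowledge of arm affects the primary endpoint, overall uptake, less directly.

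Whether the effect is trivial or serious depends on a reader shift that the documents cannot supply. At 0.10 SD it barely matters; at 0.25 to 0.50 SD it roughly doubles to quadruples the false-positive rate. The SUVmean percentages rest on the sphere model and on the assumed contrast and resolution, and the error rates on an independent-groups t-test. For an exploratory secondary endpoint this is a change that should be made, with medium confidence.

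**What to change.** Add to sections 11.2 and 8.1.2:

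1. One reader assesses all scans in random order as one batch, under codes that hide arm, scan number and clinical data.
2. The evaluability decision and its reason are made and recorded under that masking, before any lesion uptake value is extracted.
3. Target lesion and ROI are set by one written boundary rule, applied alike in both arms, and locked before arm is revealed.
4. Every injected patient is listed with the evaluability decision and reason.
5. Scans where visible post-SRS change revealed the arm are noted.

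Items 2 to 4 keep their value where masking fails.

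Cost: protocol wording and a recoded read list, with no extra scan, reader or patient. Measurement waits for batching. Because non-evaluable subjects are replaced, some replacements would be identified late and their scans read in a further short batch under the same coding. Masking will be imperfect for some post-SRS scans. With no differential shift, type I error stays at the planned 0.05, and the sample size does not change.
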